A home-based intervention to promote mindful breathing awareness through pursed-lip breathing training for COPD patients

NCT05349123

June 8, 2021

Site Principal Investigator: [name]
Protocol version number and date: June 8, 2021, Version 3

Hypothesis:

We hypothesize that providing COPD patients with a mindful breathing module that is easy-to-use, prompts them to complete daily mindful breathing practice, and provides feedback will improve their breathing mechanics, emotional awareness, increase the time that they spend in heart rate coherence, and improve their quality of life.

Aims, purpose, or objectives:

The primary outcomes of the study are changes in breathlessness and emotions. Changes from baseline to three months on the two primary outcomes will be compared between the study arms using two-sample, two-sided t-tests with 5% type I error rates. Means, SDs, medians, ranges, and frequency distributions will be reported and plotted over time by study arm. Linear models will be used to assess the impact of treatment arm on three-month outcomes after adjusting for the corresponding baseline measure and other variables related to the outcome (age, degree of breathlessness at baseline using the mMRC dyspnea, and FEV1).

Methods:

This project will involve two Phases: phase one in which mindful breathing by itself without any other device will be tested to make sure that it is acceptable to patients and makes a difference comparing to the usual protocol in use right now. Phase two will include a particular device that will guide the mindful breathing practice that we think will be more intuitive to practice and guide the mindful breathing and that device will be tested once we know that the acceptance to the mindful breathing practice, from phase one, is appropriate.

Phase 1: A total of 70 adults diagnosed with COPD will be enrolled in the study. Half of the participants will be randomized to receive the home-based PR with the Pursed Lipped Breathing Application (intervention) and half will receive the home-based PR (control). Randomization will take place in a REDCap database and will be in equal proportion.

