Phase 2: A total of 70 adults diagnosed with COPD will be enrolled in the study. Half of the participants will be randomized to receive the home-based PR with the mindful breathing module which consists of the Pursed Lipped Breathing Application and the Spire Health Tags (intervention) and half will receive the home-based PR (control). Randomization will be take place in a REDCap database and will be in equal proportion.

Both groups entail one week of baseline where the participants wear an ActiGraph activity tracker and answer questionnaires. Baseline is followed by 12 weeks of home-based PR plus health coaching. The Intervention group also has the mindful breathing module loaded on the Android tablet. Both groups will also complete questionnaires and wear an ActiGraph activity monitor at 3 and 6 months.

Questionnaires:

Quality of Life will be assessed three times (baseline, 3 and 6 months) by the Medical Research Council (mMRC) questionnaire, the Chronic Respiratory Disease Questionnaire (CRQ), the Self-Management Ability Scale (SMAS30) and the Mindful Attention and Awareness Scale (MAAS). The questionnaires take about 20 minutes to complete.

At baseline additional health data will be collected from the medical record (chart review) to complete the Charlson comorbidity index, including lung function, demographics, living condition (living alone or not), GOLD stage, and comorbidities.

ActiGraph:

Physical activity will be measured three times (baseline, 3 and 6 months) by the ActiGraph activity monitor. The ActiGraph activity monitor has tri-axial accelerometers and will be wrist worn for seven days. Important measures to be analyzed are daily number of steps, activity counts, minutes per day spent in daily physical activities of at least moderate intensity, and sedentary time (<2 metabolic equivalents).

The questionnaires and Acti Graphs will be mailed to the participant with pre-paid shipping materials to send back.

Health Coaching:

All participants will receive a weekly coaching call to discuss their rehabilitation and health process. The calls are structured using motivational interviewing. The coach will review with the patient the data from the health coach system. Collaboratively, goals for rehabilitation for the following week will be set, based on information gathered and the patients' personal preferences. Each call lasts about 20 minutes. All calls will be taped to ensure compliance with the protocol.

Target accrual: 140

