Subject population (children, adults, groups): Adults 40 years of age or older

Inclusion Criteria:

- Clinical diagnosis of COPD
- At least 10 pack years of smoking

Exclusion Criteria:

- Unable to do mild exercise (orthopedic-neurologic problems or confined to a bed)
- Unable to follow commands (cognitive impairment)
- Have a high likelihood of being lost to follow-up (active alcohol or drug abuse)
- Live in an area that does not have cellular service (Verizon)

Potential participants will have the option of meeting a study coordinator in person (if they are on campus for a clinical appointment), meeting via Video Anywhere through Epic, or meeting over the phone. If the patient desires, their consent can be digitally obtained and documented through PTRAX. The patient also has the option of receiving the consent via mail and mailing back the consent in a provided postage paid envelope. Documentation of informed consent/HIPAA authorization will involve the use of the Research Participant Tracking (PTrax) Digital Signature Capture technology for research informed consent/HIPAA authorization forms. This is an institutionally approved process for documenting consent/HIPAA authorization only while the subject, and/or the subject's representative, is in the physical presence of the person authorized to obtain consent/HIPAA authorization. The study team may print a copy of the signed consent form/HIPAA authorization form for the subject or their representative. The consent form/HIPAA authorization form will also be available to the subject via the patient portal.

Note: If the subject or their representative prefers not to use the Digital Signature Capture technology, the study team will provide a paper consent form/HIPAA authorization form for signature.

Statistica Analysis Plan

Sample Size

We calculated that sixty two participants will provide 80% power to detect 1 point of change in the two co primary outcomes (breathlessness and emotion as measured by the CRQ) with an alpha of 0.025. A 1 point change represents a clinically meaningful change.⁹⁵ We expect about a 20 percent attrition rate (withdraw, not able to complete the 12 weeks of home-based rehab) and will therefore enroll 70 participants in each phase.

Analysis Plan

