The primary outcomes of the study are changes in breathlessness and emotions. Changes from baseline to three months on the two primary outcomes will be compared between the study arms using two-sample, two-sided t-tests with 5% type I error rates. Means, SDs, medians, ranges, and frequency distributions will be reported and plotted over time by study arm. Linear models will be used to assess the impact of treatment arm on three-month outcomes after adjusting for the corresponding baseline measure and other variables related to the outcome (age, degree of breathlessness at baseline using the mMRC dyspnea, and FEV1).

The Chronic Respiratory Disease Questionnaire (CRQ) is a 20-question inventory assessing the areas of dyspnea, fatigue, emotion, and feelings of mastery. The fatigue, emotion, and mastery subscales ask patients to rate how often in the last two weeks they have been afflicted with a particular feeling or experience on a scale of 1 to 7, with higher ratings indicating less symptom impairment. The CRQ has shown to be valid and has high internal consistency reliability. Test-retest reliability is adequate in all subscales, but is particularly high in the subscales of fatigue ($r=0.90$), emotion ($r=0.93$), and mastery ($r=0.91$). The minimal clinically important difference for this instrument of 0.5 points is universally recognized. The Domains Dyspnea (breathlessness) and Emotions are the two co primary outcomes.

Physical activity will be measured at baseline, 3, and 6 months by the ActiGraph GX6 activity monitor, which has been used to assess physical activity in COPD populations. (92) The number of daily steps at baseline, 3, and 6 months and across the two groups will be compared. Emotional Intelligence will be measured by the Trait Emotional Intelligence questionnaire at baseline, 3, and 6 months .(84) Mindfulness will be measured by the Mindful Attention and Awareness Scale at baseline, 3, and 6 months.(93) The participants HRC and respiratory rate will be tracked for the entire intervention period using the Spire Health Tags. At baseline additional health data will be collected from each participant's medical record to complete the Charlson comorbidity index, including lung function, demographics, living condition (living alone or not), GOLD stage, and comorbidities.

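### The primary t-test on CRQ change uses only patients with both scores, and neither planned analysis addresses outcome-related loss that differs between arms

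*Combined protocol and SAP*

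**What the plan says.** Both the protocol's aims section and the SAP's Analysis Plan give the same primary comparison for CRQ dyspnea and CRQ emotion: "Changes from baseline to three months on the two primary outcomes will be compared between the study arms using two-sample, two-sided t-tests", at a 5% type I error rate. Both also list linear models of the 3-month outcome by arm, adjusted for the matching baseline score, age, baseline mMRC and FEV1.

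On data collection, the Methods say: "The questionnaires and Acti Graphs will be mailed to the participant with pre-paid shipping materials to send back". The CRQ is completed at baseline, 3 months and 6 months.

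On loss, the Sample Size section says: "We expect about a 20 percent attrition rate". It defines this as withdrawal or not completing the 12 weeks of rehab, and responds by enrolling 70 per phase rather than 62.

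The documents name no analysis population and give no rule for a missing 3-month CRQ. They contain no imputation, no repeated-measures model and no sensitivity analysis for missing outcomes. They do not say whether patients who stop rehab are still followed for the CRQ.

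**The concern.** The t-test on change drops every patient without a 3-month CRQ. It makes no use of that patient's baseline score or of any 6-month score. Enrolling more patients restores numbers but does not remove selection.

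Selection that differs by arm is plausible here. The outcome is self-reported and posted back, no blinding is described, and only the intervention arm has a module that prompts daily practice. If the patients who fail to return the form differ between arms in number or kind, the difference enters both co-primary estimates. The planned adjusted model handles one form of this. Nothing planned handles the other, in which return depends on how the patient has fared.

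**Working it through.** **Inputs from the documents.** 62 evaluable, 80% power, 1 point, alpha 0.025 (Sample Size); 1:1 allocation, 70 per phase, so 35 per arm; attrition about 20%; minimal important difference 0.5 points (Analysis Plan).

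**The plan's own figures.** No SD is stated, so 62 cannot be reproduced directly. Solving for the SD with 31 per arm and two-sided alpha 0.025:
- Normal approximation: 1 / [√(2/31) × (2.241 + 0.842)] = 1.28.
- Noncentral t: 1.25, used below. At the 5% level of the Analysis Plan it would be 1.38.

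If 20% of CRQ pairs were missing, 70 × 0.20 = 14 would be lost and 56 would remain. That 62/0.80 = 77.5 does not lead to 70 is a separate matter.

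**Bias formula.** Let m be the fraction missing in an arm, and g the amount by which the missing patients' mean change falls below the completers'. The all-patient mean is the completer mean minus m × g, so

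bias of the completer difference = m₁g₁ − m₀g₀ (intervention minus control).

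With the same g in both arms:
- 20/20% loss: 0 for any g.
- 25/15%: 0.10g, which is 0.05 at g = 0.5 and 0.10 at g = 1.0.
- 30/10%: 0.20g, which is 0.10 at g = 0.5 and 0.20 at g = 1.0.

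**Simulation.** Assumptions: true effect 0, 35 per arm, SD of change 1.25, moderate selection. The adjusted model conditions on baseline CRQ only. Positive values favour the intervention.

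| Loss mechanism | Loss, intervention/control | t-test on change | Baseline-adjusted model |
|---|---|---|---|
| Low baseline (intervention), random (control), correlation 0.5 | 20/20 to 30/10% | −0.12 to −0.18 | about 0 |
| Same, correlation 0.9 | 20/20 to 30/10% | −0.06 to −0.08 | about 0 |
| Poor change, both arms | 20/20% | 0 | 0 by symmetry |
| Poor change, both arms | 25/15 to 30/10% | +0.13 to +0.21 | +0.11 to +0.20 |

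**Cross-checks.**
- *Baseline mechanism.* With equal SD s at both visits, change has slope −(1 − r) on baseline and s = 1.25/√(2(1 − r)). The bias therefore scales with (1 − r)s = 1.25√((1 − r)/2), which is 0.625 at r = 0.5 and 0.280 at r = 0.9. The ratio 0.280/0.625 = 0.45 takes −0.12 and −0.18 to −0.05 and −0.08, close to the simulated values.
- *Poor-change mechanism.* If +0.13 belongs to 25/15% and +0.21 to 30/10%, the formula implies g = 0.13/0.10 = 1.3 and 0.21/0.20 = 1.05. The missing patients' mean change would be a point or slightly more below the completers'. That is fairly marked selection; a gap of half a point gives 0.05 to 0.10.

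**Scale.** 0.13/0.5 = 26% and 0.21/0.5 = 42% of the minimal important difference.

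**The case against.** The strongest reply is that the plan already contains a baseline-adjusted model of the same two outcomes. A reader might infer from the t-test alone that nothing planned corrects for selective loss. The documents do not support that: under baseline-related loss the adjusted model's bias is about 0. This part of the objection stands in full. What it leaves is that the analysis tied to a stated error rate is "two-sample, two-sided t-tests with 5% type I error rates", that the adjusted model also needs an observed 3-month CRQ, and that it stays biased when loss depends on outcome.

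A reader might also take 14 of 70 CRQs as the expected loss. The 20% is not a CRQ non-return rate: someone who stops rehab may still post the form, and someone who finishes may not. Weekly coaching calls in both arms, pre-paid return and the exclusion of people likely to be lost to follow-up may all keep non-return down.

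Nor do the documents show that the result will be biased. Bias is zero if loss is unrelated to outcome, or equal between arms in rate and in kind. Under baseline-related loss the bias runs against the intervention: false findings of benefit were under 1% against a nominal 2.5%, so the excess rejections there are false harm. The mechanisms, their strength and the correlation are all assumed. The SAP's only correlation for a co-primary domain is a test-retest value of 0.93 for emotion, which is not a 3-month trial correlation but is a reason to show a range.

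Finally, a mixed model gains little over the planned linear model if those lost at 3 months also lack a 6-month CRQ. That is a fair reason to accept either as primary.

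**Conclusion.** The concern holds in this form. The formal primary test is a complete-case comparison of change that ignores a baseline score already collected. The planned adjusted model is better but sits beside the formal test rather than in its place. No planned analysis examines loss that depends on outcome and differs by arm.

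Under the stated assumptions, the choice of the t-test over the adjusted model costs up to 0.18 points of bias if intervention-arm loss follows low baseline. Outcome-related loss at 25/15% to 30/10% could shift either analysis by roughly 0.1 to 0.2 points in favour of the intervention. These are illustrations of a risk. They rest on an SD inferred from the sample-size statement and on assumed loss rates and mechanisms. The point deserves correction before the data are seen, because the remedy is nearly free and a later choice between analyses would be post hoc.

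**What to change.** 1. Make a baseline-conditioned analysis primary for both CRQ domains. Either the linear model already planned, or a repeated-measures mixed model on baseline, 3- and 6-month CRQ that includes every randomised patient with any CRQ, will serve. Keep the t-test on change as supporting.
2. Add one delta-adjusted sensitivity analysis. Impute missing 3-month scores by multiple imputation from arm, baseline CRQ, the model covariates and any 6-month CRQ. Then lower the imputed scores in steps up to 1 point, by arm, and state where the conclusion changes.
3. Report CRQ non-return by arm, separately from rehab non-completion.

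The cost is SAP wording and a little more analysis. No new data or patients are required.

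### The two co-primary outcomes are sized at alpha 0.025 (sidedness not stated) but tested two-sided at 5%, with no success rule or multiplicity adjustment

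*Combined protocol and SAP*

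**What the plan says.** The Analysis Plan names two primary outcomes: "The Domains Dyspnea (breathlessness) and Emotions are the two co primary outcomes".

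The Sample Size section states that "sixty two participants will provide 80% power to detect 1 point of change in the two co primary outcomes", and sets the level for the "two co primary outcomes (breathlessness and emotion as measured by the CRQ) with an alpha of 0.025". It gives no sidedness, no SD and no correlation between the two domains. It does not say whether the 80% is power for each outcome, for at least one, or for both.

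For the analysis, changes from baseline to three months are to be "compared between the study arms using two-sample, two-sided t-tests with 5% type I error rates". The Aims section carries the same sentence. Adjusted models follow: "Linear models will be used to assess the impact of treatment arm on three-month outcomes".

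No section gives a success rule, a testing order, a multiplicity adjustment, or an explanation of why sizing uses 0.025 and testing uses 5%.

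**The concern.** With two primary outcomes, 0.025 is what 5%/2 gives, so the sizing looks as if it allows for two tests. The analysis text does not carry that allowance through. As written, a p-value between 0.025 and 0.05 on one outcome alone could be claimed as a positive trial, although it would miss the level used for sizing if that level is two-sided.

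Suppose dyspnea gives p = 0.04 and emotion p = 0.20. The result is positive if either outcome suffices at 5%. It is negative at two-sided 0.025 each, and negative if both are required. The plan does not say which applies, and the choice has to be made before the data are seen. The same gap affects both phases.

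**Working it through.** **Inputs from the documents.** Two primary outcomes; 62 evaluable participants, equal allocation, so 31 per arm; a 1-point effect, taken here as the between-arm difference in change; 80% power; alpha 0.025 for sizing; two-sided 5% for testing. **Assumptions, because the documents give no figure.** Correlation between the two test statistics of 0, 0.5, 0.7 or 0.9; SD of change back-solved from the stated power.

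**1. The plan's own figure.** Sample size per arm is 2 × SD² × (z_alpha + z_0.80)² / 1². With no SD stated, 62 cannot be reproduced. Solving for the SD, with √(2/31) = 0.254:

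- 0.025 two-sided: 1 / [0.254 × (2.241 + 0.842)] = 1.28; exact noncentral t, 1.25.
- 0.025 one-sided (the same as 5% two-sided): 1 / [0.254 × (1.960 + 0.842)] = 1.41; exact noncentral t, 1.38.

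Both SDs are possible, so the arithmetic does not reveal which sidedness was meant. Both take the 80% as power per outcome. If it is power for both outcomes the implied SD is smaller; if for at least one, larger.

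**2. Error if either outcome suffices.** Under independence, 1 − 0.95² = 9.75% at 5% each and 1 − 0.975² = 4.94% at 0.025 each. For correlated outcomes, the bivariate normal value of 1 − P(|Z1| < c, |Z2| < c) is:

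| Correlation | 5% each (c = 1.960) | 0.025 each (c = 2.241) |
|---|---|---|
| 0 | 9.75% | 4.94% |
| 0.5 | 9.07% | 4.65% |
| 0.7 | 8.35% | 4.30% |
| 0.9 | 7.04% | 3.62% |

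These are two-sided rates within one phase and count false findings in either direction.

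**3. Error and power if both are required.** A false claim needs significance on an outcome with no effect, so error is at most 5%. Power for joint success at two-sided 5% with 62 evaluable, from simulation over correlation 0 to 0.9:

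- SD 1.25: 76% to 84% (at independence, 0.873² = 0.76).
- SD 1.38: 64% to 75% (at independence, 0.80² = 0.64).

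The stated 80% would therefore need restating under this rule, unless it was joint power from the start.

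**4. Power at two-sided 0.025 each, 62 evaluable.**

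| | SD 1.25 | SD 1.38 |
|---|---|---|
| Per outcome at 5%, for comparison | 87% | 80% |
| Per outcome at 0.025 | 80% | 71% |
| At least one at 0.025, both effects 1 point, correlation 0 / 0.5 / 0.7 / 0.9 | 96 / 91 / 89 / 85% | 91 / 85 / 82 / 77% |

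At independence the last row is 1 − (1 − 0.800)² = 0.96 and 1 − (1 − 0.708)² = 0.91.

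**The case against.** The strongest defence is that one reading is wholly consistent. If 0.025 is one-sided it equals 5% two-sided. If co-primary means that both outcomes must be significant, error is at most 5%. If the 80% is joint power, the sizing matches that rule. This stands as a possibility, but it needs three things the plan does not state. Every stated test is two-sided. If 0.025 is two-sided, a both-required rule would give no reason to split alpha.

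A reader might infer the opposite: that the trial runs a 9.75% false-positive risk. The documents do not support that. The figure needs an either-outcome rule, which appears nowhere, and independence between two domains of one questionnaire answered by the same patients. It also counts errors in both directions; the chance of a false claim of benefit on at least one outcome is at most 1 − 0.975² = 4.94% under independence. Two-sided control is what the plan adopts, so the inflation remains on that scale, but 9.75% is a conditional ceiling.

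That each outcome is tested at 5% is the natural reading of the plural in "two-sample, two-sided t-tests with 5% type I error rates", not an explicit statement. A reader might also infer that the adjusted models compete with the t-test for primary status. The plan puts the t-test first and the models after it, so that is at most a clarification.

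**Conclusion.** The defect that needs no assumption is that the plan does not define a positive primary result and does not reconcile 0.025 in the sizing with 5% in the analysis. The consequence depends on the rule. If either outcome suffices and each is tested at 5%, familywise error per phase is about 7.0% to 9.1% at assumed correlations of 0.9 to 0.5, against 3.6% to 4.7% at two-sided 0.025 each. If both must be significant, type I error is sound, but the sizing alpha does not match the test alpha if 0.025 is two-sided, and the meaning of the 80% has to be stated.

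It would be too strong to conclude that a planned Bonferroni correction was dropped, since the documents never say one was planned. Nor does the point show that the trial is too small. In the one-sided case, 80% power for each outcome singly at two-sided 0.025 would take 76 evaluable, but under a rule of at least one significant outcome, 62 already gives 82% or more at correlations up to 0.7 if both effects are 1 point. All power figures rest on the back-solved SDs and on 62 evaluable.

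**What to change.** In the Aims section and the Analysis Plan, replace the 5% wording with one of two rules.

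- **Either outcome suffices:** *each co-primary outcome tested two-sided at 0.025 (overall two-sided type I error 5% within each phase); success if at least one is significant*. Report 97.5% confidence intervals.
- **Both are required:** say so, keep two-sided 5% for each, change the alpha in the Sample Size section to match, and restate power for joint success.

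In the Sample Size section, state the sidedness of 0.025, the assumed SD, and whether the 80% is power per outcome, for at least one, or for both; give the assumed correlation if it is not per outcome.

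The cost is text edits in three places and possibly a restated power figure; design and data collection do not change. Under the first rule, per-outcome power with 62 evaluable stays at the stated 80% if 0.025 was two-sided (SD 1.25) and falls to 71% if it was one-sided (SD 1.38). Power for at least one significant outcome, if both effects are 1 point, is 85% to 96% or 77% to 91% respectively, over correlation 0.9 to 0. If the chosen rule does not deliver the stated 80%, restate the figure rather than enrol more.
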